3.9. Removal of Patients from Treatment or Assessment

3.9.1. Early Discontinuation of the Study

The study may be discontinued at the sole discretion of the Sponsor for any reason, including medical or ethical reasons affecting the continued performance of the study, or difficulties in the recruitment of patients.

The study may also be discontinued based on evidence of either substantial efficacy, or likely failure to meet the primary objective.

3.9.2. Early Discontinuation of Individual Patients

The investigator may remove a patient from study treatment at his/her discretion for any of the following reasons:

- Disease progression
- Intolerable AE(s) or failure to tolerate the study treatment
- Patient decides to discontinue study therapy
- Any medically appropriate reason or significant protocol violation, in the opinion of the investigator
- Lost follow-up

Patients may decide to discontinue study treatment for any reason. Patients who elect to discontinue study treatment should be encouraged to continue in the study so that follow-up information on disease progression and survival status may be obtained. However, patients may elect to withdraw consent and decline further participation in the trial.

All patients will be followed until disease progression, withdrawal of consent, intolerable AEs/toxicity, death, loss to follow-up or the end of the study.

The investigator must determine the primary reason for a patient's discontinuation of study treatment and record this information on the eCRF. Patients who are prematurely withdrawn from study treatment are not eligible to re-initiate study treatment on this protocol at a later date.

4. Treatments

4.1. Identity of Investigational Product (IP)

SCB01A (a novel heterocyclic CA-4 analogue) is composed of absolute EtOH, PEG 300, and Solutol®. The average molecular weight is about 300 and conforms to the requirements of the European Pharmacopoeia monograph. Dehydrated alcohol contains > 99.2% by weight, corresponding to > 99.5% by volume at 15.56°C of C2H5OH and conforms to the requirements of the US Pharmacopoeia monograph.

SCB01A is a water insoluble, white to slightly yellow solid. At room temperature, the water solubility of SCB01A is 0.9 µg/ml. Formulated SCB01A is a sterile, clean, colorless to slightly yellow viscous solution.

4.2. Study Drug Packaging and Labeling

The study drug is packaged in glass vials with a rubber stopper and flip-off seal labeled with the study protocol number, contents, directions for use, storage directions, clinical trial statement, and sponsor name.

4.3. Study Drug Storage Conditions

Formulated SCB01A can be stored at temperatures < 30 °C. Although direct data on its photosensitivity is unavailable, the avoidance of light is recommended.

4.4. Study Drug Dose Preparation and Administration

The study drug, SCB01A is packaged as 10 mg/ml in 5 ml/vials. The injection volume of SCB01A should be calculated based on the BSA of the subject. (See section 5.1.3). The study drug will be diluted in normal saline solution before infusion. An equal volume of normal saline will be drawn out from a 250 ml normal saline container before adding the SCB01A injection solution. The total volume of study drug diluted solution will be equal to 250 ml. The study drug should be administered over a period of 3 hours by i.v. infusion through a central line in order to avoid potential extravasation and tissue necrosis. For further details, please refer to the IMP Manual.

4.5. Study Drug Accountability

Drug Accountability records will be maintained by the study sites. All used and partially used supplies of SCB01A will be destroyed by the study site in accordance with institutional policies after accountability performed by the monitor. The site will maintain detailed documentation of the number and identification of vials, which are used and destroyed, and copies of these documents will be provided to the sponsor or Clinical Research Organization (CRO). Disposition of all unused boxes of study drug will be carried out according to instructions provided by the sponsor or CRO at the end of the study and after a final drug accountability assessment is performed by the monitor.

4.6. Method of Assigning Patients to Treatment Groups

There is no randomization to be done. All patients will receive the study drug, and the dose is dependent upon the phases of the study to which the patient is enrolled. Patients will be assigned to Dose 1 initially when they enter the run-in phase of the study. Dose selection for the Phase II will be based on the occurrence of DLTs during the run-in phase and the decision made by the safety committee.

4.7. Selection of Doses in the Study

Doses were selected based on pre-clinical data and data obtained from an ongoing Phase I study as described in Section 1.2.

4.8. Selection and Timing of Dose for each Patient

The selection and timing of dose for each patient is described in Section 3.1.

Patients entered into the run-in phase will be allocated to Dose 1 to Dose 4. Dose selection for Phase II will be based on the occurrence of DTLs during the run-in phase and the decision made by safety committee on the Optimal Dose for the Phase II (see Section 3.1).

Dose 1: one i.v. administration of 3.25 mg/m² SCB01A on Days 1 and 8 of a 3-week cycle; or

Dose 0a: one i.v. administration of 5 mg/m² SCB01A on Day 1 and Day 8 of a 3-week cycle.

Dose 1a: one i.v. administration of 10 mg/m² SCB01A on Day 1 and Day 8 of a 3-week cycle.

Dose 2: one i.v. administration of 12 mg/m² SCB01A on Days 1 and 8 of a 3-week cycle; or

Dose 2a: one i.v. administration of 15 mg/m² SCB01A on Day 1 and Day 8 of a 3-week cycle

Dose 3: one i.v. administration of 18 mg/m² SCB01A on Days 1 and 8 of a 3-week cycle; or

Dose 3a: one i.v. administration of 21 mg/m² SCB01A on Day 1 and Day 8 of a 3-week cycle

Dose 4: one i.v. administration of 24 mg/m² SCB01A on Days 1 and 8 of a 3-week cycle; or

4.9. Dose Adjustment and Toxicity Management

There is no dose adjustment envisaged in this study. Where a study treatment-related Grade 3 or 4 AE occurs, the study treatment will be placed on hold until the event is resolved to grade ≤ 1 or returns to baseline before resuming the study drug. If the Grade 3 or 4 event does not resolve or return to baseline within 14 days or return to grade 3 or 4 toxicity after resuming, treatment with the study drug will cease. However the patient should be followed-up for survival analysis until the end of the study.

4.10. Blinding

This is an open-labelled study. Therefore blinding procedures are not applicable.

4.11. Prior and Concomitant Therapy

Concomitant medication is defined as any prescription or over-the-counter preparation, including vitamins, dietary supplements, and oral herbal preparations.

All medications that are taken by, or being administered to, the patient at the time of the Screening Visit, within 30 days prior to the Screening Visit, and for the duration of the study will be recorded in the eCRF.

For each medication the following will be documented:

- Medication/treatment name (generic name).
- Dose, unit, and frequency of dosing (total daily dose).
- Route of administration
- Indication for use
- The start date
- The stop date (if medication/therapy is not ongoing)

4.12. Prohibited Medications

Patients will be infused with their study treatment at the clinical site by trained personnel and the infusion start and end times will be recorded in source documents and in the eCRF

1. Any study participant that has had any investigational drug, chemotherapy, targeting agent(s), biology therapy, immunotherapy, herbal medicine or hormonal therapy administered within 4 weeks before the date of the first study treatment should be excluded from enrolment until at least 4 weeks have passed.
2. Concomitant administrations of compounds that inhibit CYP1A2 or CYP2D6 are prohibited for 3 weeks prior to study drug infusions and throughout the study. Excluded concomitant medications of CYP1A2 and CYP2D6 inhibitors include (except antibiotics whenever they are clinically indicated): fluvoxamine, ciprofloxacin, cimetidine, bupropion, cinacalcet, fluoxetine, paroxetine, quinidine¹, duloxetine, sertraline, terbinafine and amiodarone.
3. Therapy with anticoagulants, antiplatelet treatments (e.g. warfarin, heparins) are not allowed during the study

4.13. Treatment Compliance

Patients will be infused with their study treatment at the clinical site by trained personnel and the infusion start and end times will be recorded in source documents and in the eCRF.

5. Study Assessments and Procedures

5.1. Safety Procedures and Assessments

5.1.1. Medical History

Medical history will be assessed at screening and will include the following:

1. Histological or cytological confirmed metastatic squamous cell carcinoma in head and neck.

2. At least one measurable tumor lesion according to RECIST version 1.1 as assessed by the investigator (local radiological image assessment).
3. Details of the prior therapy that failed or intolerable to platinum agent and also not amenable to further surgical or radiation therapy due to disease progression or toxicity.
4. Smoking status (current smoker or past history of smoking).
5. Betel nut consumption status or history.
6. Additionally, all relevant medical histories, medical conditions, or symptoms experienced during 30 days prior to screening are to be recorded, using the body system categories outlined below. For each history, the specific medical terminology for the disease/disorder/condition, the date of diagnosis, and the history status (resolved or ongoing) will be documented.

Cardiovascular	Lymphatic
Respiratory	Hematologic
Gastrointestinal	Immunologic
Renal	Dermatologic
Hepatic	Psychiatric
Neurological	Genitourinary
Endocrine	Other

5.1.2. Physical Examination

A complete physical examination will be performed at baseline and each clinic visit prior to drug administration, if applicable and the EOT/Early Withdrawal visit to include a review of all systems. Each body system will be classified as being either normal or abnormal, with abnormalities for each body system noted. Subsequent physical examinations will identify changes from the baseline examination with both positive and negative changes being noted. The physical examination will include routine examinations for the following:

- Height (cm) (only performed at baseline)
- Weight (kg) at each visit before a study treatment infusion
- Abnormalities of the extremities
- Heart/cardiovascular abnormalities
- Musculoskeletal abnormalities
- Dermatologic abnormalities
- Neurologic abnormalities

Any other body system, for which an abnormality is noted and which, in the opinion of the Investigator, is relevant to the safety of the participant or could impact safety or efficacy results for the study patient; i.e., the abnormality is clinically significant.

5.1.3. BSA Calculation

BSA will be calculated on dosing days, using the formula below⁵:

$$\text{BSA (m}^2\text{)} = [\text{Height (cm)} \times \text{Body Weight (kg)} / 3600]^{1/2}$$

The total dose (mg) will be calculated as: Total Dose 1/Dose 2 (mg/m²) x BSA (m²)

5.1.4. Vital Signs

Vital signs will be obtained at baseline, clinic visits prior to study drug administration, if applicable and at the EOT/Early Withdrawal visit.

Vital signs will include heart rate, blood pressure, respiratory rate, and body temperature. Respiratory rate, heart rate and blood pressure (systolic/diastolic) will be obtained after the patient has been at rest for at least 5 minutes in a sitting position.

If vital sign measurements coincide with a blood sample, the vital signs will be taken prior to obtaining the blood sample.

Body temperature will be taken and recorded in degrees Centigrade.

5.2. ECOG Performance Status

The ECOG performance status will be documented at baseline and at all clinic visits.

Table 3: ECOG Performance Status Scale⁶

Grade	Descriptions
0	Normal activity. Fully active, able to carry on all pre-disease performance without restriction.
1	Symptoms, but ambulatory. Restricted in physically strenuous activity, but ambulatory and able to carry out work of a light or sedentary nature (e.g., light housework, office work).
2	In bed < 50% of the time. Ambulatory and capable of all self-care, but unable to carry out any work activities. Up and about more than 50% of waking hours.
3	In bed > 50% of the time. Capable of only limited self-care, confined to bed or chair more than 50% of waking hours.
4	100% bedridden. Completely disabled. Cannot carry on any self-care. Totally confined to bed or chair.
5	Dead.

5.3. 12-lead ECG

During the run-in phase, the 12-lead ECG will be obtained prior to study drug administration, within 1 hour following study drug administration, 2 hours after study drug administration, immediately after the 3 hour infusion, 4 hours after study drug administration, and 24 hours after administration of the drug. After cycle 4, the ECG will be obtained at every treatment cycle within 1 hour following study drug administration, and EOT/early withdrawal visit (time window: ± 5 min).

During Phase II (stage 1 and 2), the 12-lead ECG will be obtained at every treatment cycle within 1 hour following study drug administration and at EOT/Early Withdrawal visit.

The allowed time window for each ECG assessment is ± 5 min. ECGs will be obtained whenever deemed necessary at the investigator's discretion. The following ECG measurements will be recorded in the patient's source documents and on the appropriate page(s) of the eCRF:

- QRS interval
- PR interval
- QT interval
- QTc interval
- RR interval
- Investigator's interpretation of the ECG results (NOTE: for all abnormalities, the nature of the abnormality will be noted and the Investigator will comment regarding the clinical significance of the abnormality).

5.4. DCE-MRI

Tumor micro vessel density and blood flow by DCE-MRI for the patients with identified sites at both baseline and 6 hours after the 1st infusion of the drug in C1D1.

5.5. Safety Laboratory Assessments

The local laboratory for the study site will be used and all procedures will be performed following the standard operating procedure (SOP) of the local laboratory.

Hematology and clinical chemistry blood samples will be obtained at screening, all clinic visits and the EOT/Early Withdrawal visit. Coagulation will be determined at all clinic visits (excluding screening). During the run-in phase minimum of 19 samples (180 ml) will be taken. The number of sample might differ based on actual number of cycles completed and if there are any unscheduled visits done.

Urinalysis will be determined at Screening and Day 1 of each cycle prior to study treatment administration.

The parameters assessed are detailed below:

Hematology

WBC with differential, red blood cell (RBC), hematocrit (Hct), Hb, mean corpuscular volume (MCV), mean corpuscular hemoglobin (MCH), mean corpuscular hemoglobin concentration (MCHC), platelet count

Clinical Chemistry

Blood urea nitrogen (BUN), Creatinine, AST, ALT, ALP, Total Bilirubin, Albumin, Calcium, Glucose, Uric Acid, Potassium, Total creatine kinase (Ck) (if total Ck is above the ULN for the laboratory, Troponin-T or Troponin-I will be determined), gamma-glutamyl transferase (GGT). Total cholesterol, high-density lipoprotein

(HDL), low-density lipoprotein (LDL), triglycerides (TG), amylase and lipase will be tested at the Screening Visit.

Coagulation

PT, INR

Urinalysis

Specific gravity, pH, protein, glucose, leucocytes, erythrocyte, nitrite, ketone, urobilinogen, bilirubin and sediment including RBC, WBC, Hyaline, Cast, CAOX, Crystal, AMOR and mucus.

Pregnancy test

A serum beta-HCG test for women of childbearing potential will be performed \leq 14 days prior to the first dose of study treatment.

5.6. Bioanalytical Assessments

PK Procedures

PK will be performed on patients enrolled in the run-in phase.

PK blood samples will be taken immediately pre-infusion then at 2, 3, 4, 6, 10, 21 and 24 hours after start of infusion on Days 1 and 8 of Cycles 1, 2 and 3 (time window at each sample collected: ± 5 min). Sixteen (16) samples (10 mL) per cycle will be taken (480 mL during 3 cycles of the run-in phase). Also see Section 6.4 for more detail.

Biomarkers

Blood samples (10 mL) will be collected for biomarkers analysis on patients enrolled in the run-in phase; including CEC, VEGF and CEP cells.

Blood samples for biomarkers will be taken immediately pre-infusion then at 6, 10 and 24 hours after start of infusion on Day 1 of Cycle 1 and one sample during the clinic visit on Day 15 of Cycle 3 (5 samples per cycle). VEGF and CEC will be analyzed for all time points that samples were taken and CEP will be analyzed only from pre-infusion sample and the Day 15 Cycle 3 sample.

5.7. EORTC QLQ-C30

Patients will complete the questionnaire at Screening and before study drug administered, except C1D1.

The questionnaire consists of 65 questions that help determine the health outcome of the patients.

5.8. EORTC QLQ H&N35

Patients will complete the questionnaire at Screening and before study drug administered, except C1D1.

5.9. Nerve Conduction Velocity

Patients will undergo testing for the nerve conduction velocity at the following time points based on neurological symptoms:

- a. Baseline: within 30 days before C1D1 for all subjects.
- b. Within 7-30 days, since the onset for grade 2 or above neurological symptom after receiving treatment of SCB01A;
- c. Within 90-120 days, since the consent withdraw or received the last treatment of SCB01A, after the onset for grade 2 or above neurological symptom after receiving treatment of SCB01A;

The test results of nerve conduction velocity will not lead to modification of treatment schedule (i.e. Investigators do not have to wait for the test report to make decision regarding subsequent treatment continuation or modification) unless the symptom is deemed as clinical significant.

5.10. Appropriateness of Measurements

The measurements used in this in study are considered appropriate for the indication studied. Disease response is a common tool used in cancer trials to study the effectiveness of the study drug. Safety and tolerability of the study drug will be reported during the trial.

6. Safety and Efficacy Variables

6.1. Efficacy Measurements

Tumor response will be assessed by using computerized tomography (CT) or MRI scans according to RECIST v1.1 at baseline, and every 3 cycles prior to next cycle until progression of disease. For patients who meet DC criteria after the first 3 cycles of study treatment, additional radiological tumor assessments should be performed at Week 12. Any additional assessments can be arranged when clinically indicated.

Scans must include brain, chest, abdomen, and pelvis. The imaging technique used at baseline should be used throughout the study.

Survival data will be collected throughout the active treatment phase and during the follow-up period. Survival follow-up after patient discontinuation of treatment will be conducted every 3 weeks during the first 9 weeks, thereafter every 9 weeks until the end of the study. Survival rate will only be assessed in patients with measurable disease at baseline.

6.2. Dose Limiting Toxicity (DLT)

All toxicities will be classified according to the NCI Common Terminology Criteria for AEs (CTCAE) version 4.03.

DLT will be defined as the occurrence of any of the following criteria during the run-in phase, unless there is definitive alternative evidence that administration of SCB01A did not cause the specific toxicity:

- Grade 4 neutropenia exceeding 5 days' duration
- Grade 4 thrombocytopenia
- Grade 4 anemia
- Grade 3 or greater neutropenia with complications (e.g., fever, infection etc.)
- Grade 3 or greater thrombocytopenia with complications (e.g., bleeding)
- Grade 3 or greater non-hematological AEs including Grade 3 unmanageable nausea and vomiting that persist for 3 or more days after drug administration. Grade 3 fatigue lasting for \leq 1 week is not considered as a DLT
- Grade 3 or greater prolonged QTc interval
- Grade 3 or greater neurotoxicity
- Delayed treatment exceeding 14 days duration due to drug-related toxicity.

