Study Objectives:	
Objective:
 
The study is designed with a run-in phase and the continuation phase (Phase II) is to evaluate the safety and efficacy of SCB01A in patients with recurrent or metastatic squamous cell carcinoma of head and neck.
 
Run-in phase
 
Primary Objective:
 
To determine the optimal dose for 3 cycles of i.v. administration of SCB01A on Days 1 and 8 of each cycle in a 3-week cycle
 
Secondary Objective:
 
To evaluate the safety and toxicity for 3 cycles of i.v. administration of SCB01A on Days 1 and 8 of each cycle in a 3-week cycle
 
Phase II
 
Primary Objective:
 
To assess the disease control rate (DCR) at the end of the 9th week (3 cycles, each cycle consists of 21 days) after treatment with SCB01A, according to the Response Evaluation Criteria in Solid Tumors (RECIST) version 1.1.
 
Secondary Objectives:
 
 • To assess the overall survival (OS) rate at 36 weeks after first treatment with SCB01A in patients with recurrent or metastatic squamous cell head and neck cancer who have previously been treated with platinum therapy. • To assess the progression-free survival (PFS) • To assess the PK profile of SCB01A of patients in the run-in phase. • To assess health outcomes using patient-reported European Organization for Research and Treatment of Cancer Quality of Life Questionnaire-C30 (EORTC QLQ-C30) and EORTC QLQ H&N35 questionnaires. • To assess biomarkers relevant to the efficacy and mechanism of action of SCB01A. • To explore the possible association between biomarkers and clinical outcomes
Study Design:	Multicenter, open-label, phase II study of SCB01A administered to patients with recurrent or metastatic squamous cell carcinoma of head and neck. The study will be conducted in two parts.
	Run-in Phase I (Dose Escalation Phase):

The first part of the study involves dose-escalation, in which successive cohorts of three patients (expanded to six patients in the event of a dose-limiting toxicity) will receive escalating doses of SCB01A until 24 mg/m². Dose escalation assessment will be based on tolerability observed during 3 cycles of treatment. An Optimal Dose will be agreed upon.

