During the run-in phase, three patients will be enrolled and will receive 3 cycles of i.v. administration of SCB01A at a dose of 3.25 mg/m² (Dose 1) on Days 1 and 8 of each cycle in a 3-week cycle (Dose 1). If 1 of the three patients experiences a dose limiting toxicity (DLT) during the first 3 cycles, an additional three patients will be enrolled at the same dose level. If 0/6 or 1/6 i.e. ≤ 1 of subjects experienced DLT at the given dose level, the dose of the subsequent cohort will be increased to the next level, then this process will continue until $>1/6$ of subjects experience DLT at certain dose level or the maximum dose in this protocol, 24 mg/m² (Dose 4) is reached.

Patients enrolled in the run-in phase must either complete 3 cycles of study treatment or experience a DLT to be included in the Full Analysis Set (FAS) for the statistical analyses. During the run-in phase, patients who do not complete the 3 cycles of study treatment, and who do not experience a DLT, will be replaced.

Rules for dose escalation for the run-in phase of the study are listed as following:

1. Dose level will start at 3.25 mg/m² (Dose 1) in the 1st Cohort and can be escalated to 12 mg/m² (Dose 2), 18 mg/m² (Dose 3) and 24 mg/m² (Dose 4). If ≤ 1 subjects have DLT in a cohort of 24 mg/m² (Dose 4), the 24 mg/m² (Dose 4) will be determined as the Optimal Dose.
2. If $=1/3$ subjects in a cohort have DLT(s), enrol three more subjects at the same dose level or if ≤ 1 subjects (i.e., 0/3 or 1/6) experience DLT then subjects can be enrolled into the next higher dose level as per below:
 - a) **Dose Level 3.25 mg/m² (Dose 1):** This dose level has been completed as part of protocol amendment #2 and ≤ 1 patient experienced DLT. Patients will be enrolled in the next dose level based on results from 3.25 mg/m² (Dose 1) Cohort.
 - b) **Dose Level 12 mg/m² (Dose 2):** If 1 patient experiences DLT then 3 additional patients to be enrolled in the same dose level. If the total DLT from 6 patients at the same dose level is ≤ 1 , then the study to move to the next higher dose level. If >1 patients have DLT, then 3 patients to be enrolled at the reduced dose of 10 mg/m² (Dose 1a).

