--	---

[figure not shown]

Figure 1: Schematic Study Design

All patients will be treated until the occurrence of progressive disease, intolerable adverse events (AEs)/toxicity, consent withdrawal or death. After discontinuation of study treatment, all patients will be followed for survival and disease-specific therapies of the clinician's choice will be administered. Follow-up visits will be scheduled every 3 weeks for 9 weeks, thereafter every 9 weeks until the end of the study.

The study will be completed 36 weeks after the last patient has received their 1st treatment with SCB01A.

Dose Limiting Toxicity (DLT) definition (in run-in phase)

- All toxicities will be classified according to the National Cancer Institute (NCI) Common Terminology Criteria for AEs (CTCAE) version 4.03. DLT will be defined as the occurrence of any of the following criteria unless there is definitive alternative evidence that administration of SCB01A did not cause the specific toxicity:
 1. Grade 4 neutropenia exceeding 5 days duration;
 2. Grade 4 thrombocytopenia;
 3. Grade 4 anemia;
 4. Grade 3 or greater neutropenia with complications (e.g., fever, infection, etc.);
 5. Grade 3 or greater thrombocytopenia with complications (e.g., bleeding);
 6. Grade 3 or greater non-hematological AEs including Grade 3 unmanageable nausea and vomiting that persist for 3 or more days after drug administration. Grade 3 fatigue lasting for ≤1 week is not considered as a DLT;
 7. Grade 3 or greater prolonged QTc interval;
 8. Grade 3 or greater neurotoxicity;
 9. Delayed treatment is exceeding 14 days duration due to drug-

	
related toxicity.
 
Safety Monitoring Committee (SRC)
 
The SRC, composed of the principle investigators at each participating site, an independent medical monitor (physician experienced in oncology studies), and medical and safety representatives of the Sponsor, will be responsible for making decisions regarding dose escalation, determining the recommended dose, and starting enrollment of cohort expansions. Serial assessments of PK results also may be taken into account for the determination of the MTD and Optimal Dose.
 
Safety Monitoring Committee will meet after completion of Each Cohort in the Run-in Phase and after the completion of Phase II stage 1.
 
MTD Definition
 
The MTD is defined as the dose immediately preceding the dose level at which DLTs are observed in 2 or more patients.

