3.1. Description of Overall Study Design and Plan

This study is a single arm, open-label, Phase II trial. There will be two phases in this study, the run-in phase and the continuation phase (Phase II). Phase II will consist of 2 stages.

Run-in Phase

During the run-in phase, three patients will be enrolled and will receive 3 cycles of i.v. administration of SCB01A at a dose of 3.25 mg/m^2 on Days 1 and 8 of each cycle in a 3-week cycle (Dose 1). If one of the three patients experienced a Dose Limiting (DLT) during the first 3 cycles, an additional three patients will be enrolled at the same dose level (Dose 1). If ≤ 1 of subjects experienced DLT at the given dose level, the dose of the subsequent cohort will be increased to the next level, then this process will continue until $\geq 2/3$ or $2/6$ of subjects experience DLT at certain dose level or the maximum dose(Dose 4) in this protocol, 24 mg/ m^2 is reached.

Rules for dose escalation for the run-in phase of the study are listed as following:

1. If 0/3 subjects have a DLT, escalate to the next higher dose level with a cohort of three subjects, unless the maximum dose to be tested in this study, i.e. 24 mg/m^2 (Dose 4). If 0/3 subjects have DLT in a cohort of 24 mg/m^2 (Dose 4), the 24 mg/m^2 (Dose 4) will be determined as the Optimal Dose.
2. If 1/3 subjects have DLT(s), enrol three more subjects at the same dose level:
 - a) If the dose for the cohort is less than 24 mg/m^2 (Dose 4) and 1/6 subjects have DLT(s), escalate to the next higher dose level;
 - b) If the dose for the cohort is higher than 3.5 mg/m^2 (Dose 1) and $> 1/6$ subjects have a DLT, de-escalate to the next dose level (0a, 1a, 2a or 3a) with 3 subjects .
 - c) If > 1 out of 6 subjects in the next lower dose (0a, 1a, 2a or 3a) have DLT(s), then the previous dose will be defined as the MTD.
 - d) If ≤ 1 out of 6 subjects in the next lower dose (0a, 1a, 2a or 3a) have DLT(s), then that dose will be defined as the Optimal Dose.
3. If the dose for the cohort is 24 mg/m^2 (Dose 4) and $1 \leq 6$ subjects have a DLT, then the dose level of 24 mg/m^2 (Dose 4) will be determined as the Optimal Dose.

Patients enrolled in the run-in phase must either complete 3 cycles of study treatment or experience a DLT to be included in the Full Analysis Set (FAS) for statistical analyses. During the run-in phase, patients who do not complete the 3 cycles of study treatment, and do not experience a DLT, will be replaced.

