6.3. Safety Measurements

The following safety assessments will be done during the study:

- Incidence and intensity of AEs evaluated using the CTCAE version 4.03
- Incidence and intensity of clinically significant abnormal laboratory values evaluated using the CTCAE version 4.03
- Percentage of patients experiencing dose adjustments, including delays or discontinuation of study medication
- Physical examination findings
- Vital signs measurements
- ECG (including PR, QRS, QT, QTc and RR intervals) findings

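### The DLT list has no item for the permanent discontinuation that Section 4.9 requires when toxicity recurs, so a few run-in toxicity stops may fall outside the written DLT count

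*Protocol*

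**What the plan says.** **DLT list.** Section 6.2 ends its list with "Delayed treatment exceeding 14 days duration due to drug-related toxicity". The synopsis carries the list twice: under Criteria for Evaluation with the same item, and under Study Design as "Delayed treatment is exceeding 14 days duration", again tied to drug-related toxicity. None of the three names permanent discontinuation. Among the blood-count items, neutropenia counts if it is Grade 4 for more than 5 days, or under "Grade 3 or greater neutropenia with complications (e.g., fever, infection etc". Thrombocytopenia counts at Grade 4, or at Grade 3 with complications such as bleeding. Anemia counts at Grade 4.

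**Stopping rules.** Section 4.9 envisages no dose adjustment. A related Grade 3 or 4 event puts treatment on hold until it falls to Grade 1 or lower or returns to baseline. Treatment ends if that takes more than 14 days, or if Grade 3 or 4 toxicity comes back after resuming. Section 3.9.2 also lets the investigator stop a patient for intolerable events, with no grade threshold.

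**Counting and replacement.** Section 3.1 says "If 0/3 subjects have a DLT, escalate to the next higher dose level with a cohort of three subjects", allows escalation at 1/6, and says "patients who do not complete the 3 cycles of study treatment, and do not experience a DLT, will be replaced". The synopsis has the same replacement rule.

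**Stated basis of escalation.** The synopsis says "Dose escalation assessment will be based on tolerability observed during 3 cycles of treatment".

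**The concern.** A stop for drug toxicity within the first three cycles is direct evidence on the run-in's primary question, which is the optimal dose for three cycles. If that stop matches no DLT item, the replacement rule takes the patient out of the cohort and puts in another. The patients removed are selected for having tolerated the drug poorly, so the written count errs towards escalation.

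Delay and discontinuation are not obviously the same event in this protocol. Section 6.3 lists "Percentage of patients experiencing dose adjustments, including delays or discontinuation of study medication", naming the two separately. At stake is whether a cohort passes, expands to six or stops, and so which dose would be carried into Phase II.

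**Working it through.** **Step 1: can a stop required by the protocol match no DLT item?** Take a related event that leads to a hold, resolves within 14 days, allows treatment to resume, and then recurs at Grade 3 or 4 within Cycles 1-3. Section 4.9 ends treatment.

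| Recurring event | DLT item met? |
|---|---|
| Grade 3 neutropenia, no complication | No |
| Grade 4 neutropenia, 5 days or less, no complication | No |
| Grade 3 thrombocytopenia, no complication | No |
| Grade 3 anemia | No |
| Grade 4 thrombocytopenia or anemia | Yes, at first occurrence |
| Grade 3 or greater non-hematological event | Generally yes, at first occurrence; Grade 3 fatigue of a week or less is excluded |

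The hold lasted no more than 14 days, so the delay item is not met before the stop. It is met afterwards only if a permanent stop is read as a delay. The other route in Section 4.9, failure to resolve within 14 days, uses the same limit as the delay item and is broadly aligned with it. The gap is therefore essentially the first four rows.

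**Step 2: what happens to the patient?** There is no completed third cycle and no listed DLT. Under Section 3.1 the patient is replaced. Under protocol Section 8.3 the patient is also outside the Full Analysis Set.

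**Step 3: illustrative size.** The plan gives no operating figure for the run-in to reproduce; SAP Section 2.4 calls its sample size empirical. The documents also give neither a DLT rate nor a rate of unlisted stops, so both inputs are assumptions:

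- *d* = risk of a listed DLT, set at 0.15;
- *s* = risk of a toxicity stop with no listed DLT, from 0 to 0.10;
- no committee override, and a delay item that catches none of these stops.

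A level passes with 0/3, or with 1/3 followed by 0/3:

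P(pass) = (1 − p)³ + 3p(1 − p)⁵.

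As written, the stops are replaced, so p = d/(1 − s). If the stops count, p = d + s.

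| s | p as written | Pass as written | p if counted | Pass if counted | Gap (points) |
|---|---|---|---|---|---|
| 0 | 0.1500 | 81.4% | 0.15 | 81.4% | 0 |
| 0.01 | 0.1515 | 81.1% | 0.16 | 79.3% | 1.7 |
| 0.03 | 0.1546 | 80.4% | 0.18 | 75.2% | 5.3 |
| 0.06 | 0.1596 | 79.4% | 0.21 | 68.7% | 10.7 |
| 0.10 | 0.1667 | 78.0% | 0.25 | 60.0% | 18.0 |

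Worked row, s = 0.03. As written, p = 0.15/0.97 = 0.1546, giving 0.6041 + 0.2003 = 0.8044. Counted, p = 0.18, giving 0.5514 + 0.2002 = 0.7516. Gaps are taken from unrounded values.

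**Sensitivity.** At s = 0.03 the gap is 4.8 points for d = 0.10 (90.1% against 85.3%) and 5.2 points for d = 0.20 (69.5% against 64.3%). If the delay item already catches half of s = 0.06, the as-written p becomes 0.18/0.97 = 0.1856 and pass is 74.0% against 68.7%, a gap of 5.3 points. Because the route in Step 1 is narrow, the upper rows for s should not be read as likely.

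**The case against.** **The committee decides, not the count.** The synopsis makes the safety committee responsible for escalation and has it meet after each run-in cohort. Section 3.1 has it evaluate all run-in adverse events. Section 7.2 requires every adverse event leading to permanent withdrawal to be discussed with the medical monitor, at any grade, and a medical monitor sits on the committee. One of the synopsis escalation rules is worded permissively. This stands. A reader might infer that these patients never weigh against escalation, but the documents do not support that. What is missing is a written rule on how to count them, while the replacement sentence points towards not counting.

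**A permanent stop is a delay of more than 14 days.** This is a reasonable reading and may cover some stops. The DLT list does not say so, however, and Section 6.3 names the two separately, although that section is a list of safety summaries and does not define a DLT. If the reading was intended, the rewording only makes it explicit.

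**Lower-grade stops.** A reader might go further and want every investigator-judged lower-grade stop to be an automatic DLT. The documents do not require this. The list rests mainly on grade thresholds, and two discretionary Grade 2 stops would then end escalation at a level and place the maximum tolerated dose below it, with a risk of under-dosing. That trade-off belongs to the committee.

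**The size is assumed.** This is correct. The table shows direction and scale under stated inputs and is not evidence about this trial.

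**Conclusion.** The concern holds in a narrow form. Section 4.9 can require a permanent stop for recurrent toxicity that matches no item in any of the three DLT lists, and the replacement rule then removes that patient from the written count. The affected cases are mainly recurrent uncomplicated Grade 3 cytopenia and short uncomplicated Grade 4 neutropenia.

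The effect on the chance of passing a level is zero if such stops do not occur. It is about 2 to 5 points at assumed rates of 1% to 3%, before any committee judgement, which would reduce it. Larger gaps need rates that nothing in the documents supports.

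It would be tempting to infer that a dose in this trial was escalated wrongly. The documents report no such stop. The SAP (Sections 1 and 2.1) records termination in the run-in with five patients enrolled, only Doses 1 and 2 opened, and no Phase II recruitment. SAP Section 4 puts all enrolled run-in patients in the Full Analysis Set, and the listing of early drug discontinuation is kept. These affect reporting and leave the DLT rule as it was. Severity: minor.

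**What to change.** Reword the last DLT item in Section 6.2 and in both synopsis lists to: *Delayed treatment exceeding 14 days, or permanent discontinuation of SCB01A required under Section 4.9 during Cycles 1-3, due to drug-related toxicity.*

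Next to the replacement rule in Section 3.1 and the synopsis, add that a run-in patient who stops for lower-grade drug-related intolerance is replaced only after the safety committee has decided whether the stop counts as a DLT. The replacement rule already exempts patients with a DLT, so stops under Section 4.9 need no further wording there.

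**Cost.** One item changes in three places, and one sentence is added in two. No new data are needed, because Section 3.9.2 already has the primary reason for discontinuation recorded on the eCRF. Some cohorts may expand to six or stop sooner, and the committee may have to rule on a patient before its scheduled end-of-cohort meeting.
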